Mynosys clinical study trained personnel and / or personnel from a Contract Research Organization will monitor all clinical studies in a manner consistent with any applicable health authority regulations and the clinical research standards adopted by the Mynosys clinical

department. Mynosys clinical study trained personnel and / or personnel from a Contract Research Organization will:

1. Meet with investigator(s) prior to the initiation of the study to review the adequacy of the subject population, facilities, and equipment with respect to the needs of the study; to familiarize the investigator with the study protocol; and to reinforce GCP guidelines for clinical study conduct.
2. Conduct interim monitoring visits and telephone consultation as necessary during the course of the study to ensure the proper progress and documentation of the study findings.
3. Visit the clinical site when all subjects have completed the final visit of the study to collect the CRFs.

XIV. APPENDICES

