A successful complete Zepto™ capsulotomy is defined in this protocol to be one that results in a complete 360° capsulotomy without any residual tissue bridges visible to the surgeon. If there are such tissue bridges, the surgeon completes the capsulotomy manually.

Effectiveness Rate – An effectiveness rate of 95% complete capsulotomies provides reasonable assurance that the Zepto™ system is effective.

Data Recording - The presence of a complete capsulotomy without tissue bridges will be recorded by the surgeon as a Yes or No following each Zepto™ capsulotomy.

B. Primary Safety Endpoint - Posterior Capsular Rupture & Vitreous Loss (4% or less)

Clinical Discussion - Posterior capsular rupture & vitreous loss is generally considered one of the most significant complications of cataract surgery that occurs with some frequency. One well recognized cause is posterior extension of an anterior capsular radial tear. It is noteworthy however, that the majority of anterior capsular tears do not

adversely impact visual outcome.³ Posterior capsular rupture and vitreous loss subject the patient to additional risks of postoperative complications commonly resulting in suboptimal best corrected visual acuity, and usually precludes intracapsular IOL fixation. Due to its potential adverse impact on best corrected visual acuity, posterior capsular rupture and vitreous loss related to Zepto™ capsulotomy is chosen as the primary safety endpoint.

Posterior Capsule Rupture & Vitreous Loss Rate – The incidence of posterior capsular rupture and vitreous loss has been documented in 13 peer-reviewed publications over the period between 1999-2011. With one exception, all of these studies have shown rates ranging from 1.1 to 4.4 percent depending on surgeon group ⁴⁻¹⁶. A posterior capsular rupture and vitreous loss rate within the range of this published data in subjects receiving Zepto™ capsulotomies will provide reasonable assurance that the Zepto™ capsulotomy system acceptably meets the safety endpoint in the proposed study.

Data Recording – The occurrence of a posterior capsular rupture and vitreous loss will be recorded by the surgeon as a Yes or No following the completion of surgery.

C. Other Parameters To Be Captured

- 1) Anterior Capsule Tear – The occurrence of an anterior capsule tear will be recorded by the surgeon as a Yes or No after the completion of Zepto™ capsulotomy.

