- Possibly: Any untoward medical occurrence reported in a subject, user or other person, which might have a direct or indirect relationship to the study device/study protocol, including any malfunction, failure, deterioration in the characteristics or deployment and/or performance of the device, as well as any inadequacy in the labeling or the instructions for use and an alternative cause is equally or less likely compared to the potential relationship to the study device/study protocol.
- Unlikely: Any untoward medical occurrence reported in a subject, user or other person, which might have a little relationship to the study device/study protocol, including any malfunction, failure, deterioration in the characteristics or deployment and/or performance of the device, as well as any inadequacy in the labeling or the instructions for use and a likely alternative cause exists.
- Unrelated: Any untoward medical occurrence reported in a subject, user or other person, which has no direct or indirect relationship to the study device/study protocol, and a more likely alternative cause (underlying or concurrent illness, effect of another procedure/device/drug) is identified or strongly suspected.

D. Reporting

1. On-Site Serious Adverse Event (SAE) Reporting

The site should report any event to the Sponsor in an expedited manner if it meets the criteria for an SAE, or Serious Adverse Device Effect. Expedited reporting is calling, e-mailing, or faxing the Sponsor within 24 hours of becoming aware of the event. When calling or e-mailing the Sponsor to report an SAE or Serious Adverse Device Effect, the site should forward any supporting documents along with the SAE Report Form to the Sponsor within 24 hours of the initial call or e-mail and follow-up with CRF submission within 3 working days of identification. When faxing the notification and supporting documentation, the SAE Report should be included. Refer to the Personnel and Facilities section for Sponsor contact information for reporting of SAEs and Serious Adverse Device Effects. Sites must also report these events to the reviewing EC/IRB per their established reporting procedures.

2. Off-Site Serious Adverse Event (SAE) Reports

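### The sentence choosing the primary safety endpoint limits it to ruptures related to Zepto capsulotomy, while the rest of the protocol states it without that limit

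*Protocol*

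**What the plan says.** Section VI.B of the protocol selects the endpoint in its Clinical Discussion paragraph: "posterior capsular rupture and vitreous loss related to Zepto™ capsulotomy is chosen as the primary safety endpoint". The other statements of the endpoint do not carry that condition:

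- **VI.B heading:** "Primary Safety Endpoint - Posterior Capsular Rupture & Vitreous Loss (4% or less", with 4% as the limit.
- **VI.B, rate paragraph:** reasonable assurance of safety is to come from "A posterior capsular rupture and vitreous loss rate within the range of this published data in subjects receiving Zepto™ capsulotomies". The benchmark is introduced with the words "The incidence of posterior capsular rupture and vitreous loss has been documented in 13 peer-reviewed publications" and, with one exception, runs from 1.1 to 4.4%.
- **VI.B, Data Recording:** "The occurrence of a posterior capsular rupture and vitreous loss will be recorded by the surgeon as a Yes or No", once surgery is complete.
- **XI.B:** the precision statement assumes a 4% rate in 100 eyes, with no reference to cause.
- **Appendix 2 and Appendix 3.E:** posterior rupture is an item the surgeon observes during surgery, with no attribution step.

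Section X.C.2 separately has the investigator grade the relationship of each adverse event to the device and procedure as Probably, Possibly, Unlikely or Unrelated. Section XII rules out hypothesis testing and bases the evaluation of safety on the point estimate and its exact confidence interval.

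**The concern.** The protocol describes two possible numerators for one primary rate: all eyes with rupture and vitreous loss, or only those in which the event is attributed to the capsulotomy.

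The study has no control group. The observed rate is read directly against 4% and against a published incidence that the protocol describes without limit by cause. A related-only count can never exceed the all-event count, so any difference between the two favours the device. The difference would also rest on unblinded investigator judgement. The same data could therefore produce two primary safety rates, and the protocol's text supports either one, though not equally.

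**Working it through.** **1. Are the two counts really different?** Yes, on the protocol's own account. VI.B says "One well recognized cause is posterior extension of an anterior capsular radial tear", which implies other causes. Section VII has the capsulotomy followed by conventional phacoemulsification and lens implantation, and the Yes/No item is completed after surgery, so it captures a rupture from any step. X.C.2 expressly provides for competing causes. Its grade Possibly applies where "an alternative cause is equally or less likely compared to the potential relationship to the study device/study protocol", and its grade Unlikely covers an event "which might have a little relationship to the study device/study protocol". Neither grade is tied to the endpoint, so under a related-only reading at least these two are open to either treatment.

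**2. Reproducing the protocol's figure.** Inputs from XI.B and XII: n = 100, 4 events, two-sided 95% Clopper-Pearson interval.

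- Lower limit = Beta quantile(0.025; 4, 97) = 1.10%
- Upper limit = Beta quantile(0.975; 5, 96) = 9.93%

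This matches XI.B. The stated interval is correct for 4 counted events, whichever definition produced them.

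**3. What one event does.** Suppose 5 ruptures with vitreous loss occur and 1 is judged unrelated.

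- Counting all: 5/100 = 5%, interval 1.64 to 11.28%.
- Counting related only: 4/100 = 4%, interval 1.10 to 9.93%.

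The point estimate moves from above 4% to 4%. Both intervals contain 4%, so only the point estimate changes side.

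**4. Size across the protocol's own range.** Let p be the true rate from any cause and s the share of events judged related, each event being judged independently. The related count is then Binomial(100, p × s), and

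P(4 or fewer) = Σ (k = 0 to 4) C(100, k) (ps)^k (1 − ps)^(100 − k).

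The values of s are assumptions, since the protocol gives no share. The values of p stay within 1.1 to 4.4%.

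| True rate p | All count (s = 1) | s = 0.75 | s = 0.50 | Gain in points (0.75 / 0.50) |
|---|---|---|---|---|
| 1.1% | 99.5% | 99.9% (ps = 0.825%) | 100.0% (ps = 0.55%) | 0.4 / 0.5 |
| 2% | 94.9% | 98.2% (ps = 1.5%) | 99.7% (ps = 1.0%) | 3.3 / 4.7 |
| 4% | 62.9% | 81.8% (ps = 3.0%) | 94.9% (ps = 2.0%) | 18.9 / 32.0 |
| 4.4% | 54.9% | 76.5% (ps = 3.3%) | 93.0% (ps = 2.2%) | 21.5 / 38.0 |

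The gains are taken from unrounded probabilities. The effect is negligible at the bottom of the range and material at the top.

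**The case against.** The strongest reply is that the phrase is loose wording for rupture in eyes that had a Zepto capsulotomy. It stands in explanatory text, while every operational passage (heading, recording rule, sample size, appendices) is unrestricted. The next paragraph describes the rate as one in subjects receiving the procedure, which is a population and not an attribution. Nothing in the protocol tells anyone to filter the Yes/No item by cause, so following the recording and analysis text gives the all-event count.

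Most of this stands: the unrestricted reading is the better supported one. It does not remove the contradiction, because the qualified sentence is the one that chooses the endpoint, and relatedness is a graded concept elsewhere in the protocol that a reader could apply literally.

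Four further points are fair:

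- How the 13 publications counted ruptures cannot be seen, so a mismatch with the benchmark rests only on the protocol's own unqualified description.
- The larger gains in the table need both a high true rate and a substantial share of ruptures discounted.
- The table treats 4% as a cut-off for the point estimate, whereas section XII evaluates the estimate together with its interval.
- Posterior capsule rupture is a mandatory adverse event under X.B, with its relationship assessed, and specific adverse events are tabulated under XII. The total would stay visible even if the primary rate were the smaller one.

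Which causality grades would count as related is something a statistical analysis plan could settle, so that is not held against the protocol.

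**Conclusion.** The inconsistency is real and concerns the definition of a primary endpoint. No stated figure is wrong, and neither intent nor actual bias is shown. The consequence is conditional: if the choosing sentence is applied as written, the primary safety rate can be lower than the all-event rate and cannot be higher. Under the assumed shares of 75% and 50% related, the chance of an observed rate of 4% or less rises by under 1 point at a true rate of 1.1%, and by roughly 19 to 38 points at true rates of 4 to 4.4%. One reclassified event is enough to bring 5% down to 4%. With no test and no control group, that is enough to call for correction, although the adverse event tables limit the harm.

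**What to change.** In VI.B, delete the four words that tie the event to the capsulotomy. That alone reconciles the passages. To prevent the question returning, add: *Every occurrence of posterior capsular rupture and vitreous loss in a study eye counts toward the primary safety rate, whatever its cause. The investigator's relatedness assessment is reported as supportive information only.*

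The cost is one wording change. Occurrence is already recorded without regard to cause, so no new data are needed, and the 100 eyes and the 1.10 to 9.93% interval stay as they are. The downside for the sponsor is a possibly less favourable observed rate, because ruptures arising from other surgical steps also count.

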- 2) Corneal Touch - The occurrence of corneal touch by the Zepto™ capsulotomy tip during its use will be recorded by the surgeon as a Yes or No after the completion of Zepto™ capsulotomy.
- 3) Capsulotomy Diameter – The diameter of the Zepto™ capsulotomy will be measured during surgery by the surgeon using an intraocular rhesis ruler.

VII. STUDY DESIGN

This study is a prospective, non-randomized, multi-site clinical study with up to 8 clinical sites enrolling a total of 100 eyes of subjects aged 22 and older, who will have Zepto™ capsulotomy followed by conventional phacoemulsification and IOL implantation.

Subjects will be screened for eligibility and informed consent will be obtained from those who meet screening criteria and are interested in participation in the study. Eligible subjects will be examined preoperatively to obtain a medical history and to establish a baseline for ocular condition. Baseline measurements will be collected as outlined in Section IX.

VIII. SUBJECT POPULATION

Subjects with symptomatic age-related lens cataract desiring lens extraction and IOL implantation.

A. INCLUSION CRITERIA

1. Subjects must be age 22 or older,
2. Subjects consenting to undergoing phacoemulsification and IOL implant surgery for the treatment of symptomatic age related lens cataract, and then electing to undergo Zepto™ capsulotomy,
3. Subjects must be willing and able to return for scheduled treatment and follow-up examinations for 1 month.

B. EXCLUSION CRITERIA

1. Disease or pathology in the treatment eye that will compromise visual performance or refractive outcome (e.g. previous refractive surgery),
2. Zonular abnormality,
3. Posterior polar cataract,
4. Fellow eye with acuity less than 20/200,
5. Any prior ocular surgery of the study eye,
6. Advanced glaucoma (greater than 0.8 cup: disk) or intraocular pressure \geq 30 mmHg in the study eye,
7. Pupillary dilation during the pre-operative exam of less than 7 mm in diameter,
8. Proliferative diabetic retinopathy,
9. Disorders of the ocular muscles, such as nystagmus or strabismus,
10. Chronic uveitis,
11. Abnormal corneal endothelium,
12. Subjects on medications with, in the opinion of the surgeon, significant ocular side effects,
13. Pregnant or nursing (lactating) women,
14. Implanted ocular device or drug in the study eye,

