A Zepto™ capsulotomy is performed by applying suction to the suction cup causing the nitinol ring to be apposed to the lens capsule. A series of 12 electrical pulses lasting a total of 4 milliseconds is delivered to the nitinol ring causing rapid phase transition of water molecules trapped between the bottom edge of the nitinol ring and the capsule. The rapid volume expansion results in the capsule cutting action. Suction is then vented to atmosphere. The operating assistant will, upon command from the physician, introduce a small amount of Balanced Salt Solution (BSS) into the suction cup to allow for a gentle release of the suction cup from the capsule, and to allow the free-floating capsule button to stay behind in the anterior chamber for manual removal with forceps. Upon completion of the capsulotomy, the disposable Zepto™ Handpiece tip is removed from the eye.

E. ZEPTO™ CAPSULOTOMY PROCEDURE

The Zepto™ capsulotomy will be performed on Day 0 of the study according to the following instructions:

1. Patient Preparation
 - 1.1. Obtain preoperative dilation per standard protocol.
 - 1.2. Obtain anaesthesia per standard protocol.
 - 1.3. Clean the subject's eyelids and ocular adnexa with disinfecting solution.
 - 1.4. Apply sterile drapes.
2. Zepto™ System Setup
 - 2.1. Ensure that the red 'Emergency Off' button is in the 'Out' position.
 - 2.2. Plug the female end of the Zepto™ Power Cord into the rear of the Zepto™ Power Console, and then plug the male end of the power cord into a properly grounded electrical outlet.
 - 2.3. Make sure the area around the electrical outlet is clear and easily accessible, in case there is a need to unplug the Zepto™ Power Console from the outlet.
 - 2.4. Make sure that the electrical outlet that you use is not controlled by a light switch, and do not use an extension cord that has a switch. The Zepto™ Power Console must remain powered on at all times to work properly.
 - 2.5. Turn on power for the Zepto™ Power Console using the small switch located on the rear power entry module where the power cord plugs in. The Zepto™ Power Console will perform a self-check. A successful Zepto™ Power Console self-check will result in a flashing green Status light.
 - 2.6. Open the package, and pass the Fluid Isolator to the operating attendant.
 - 2.7. Aseptically remove the Mynosys disposable Zepto™ Handpiece from the outer pouch and aseptically transfer the inner pouch to the scrub nurse.

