- 3.12. Instruct assistant to introduce small amount of pre-loaded BSS into the suction cup to gently release the suction cup from the capsule (this is done by the assistant moving a roller clamp on the suction tubing).
- 3.13. Stabilizing the eye with the Thornton fixation ring, remove the Zepto™ Handpiece capsulotomy tip from the anterior chamber by manually withdrawing it through the corneal incision. The Zepto™ capsulotomy tip automatically folds and conforms to the incision as it is withdrawn from the eye.
- 3.14. The excised capsule “button” (circular piece of capsule tissue that has been cut) from the capsulotomy will be free-floating within the anterior chamber and can be retrieved by forceps.
- 3.15. In the event of an incomplete capsulotomy with remaining tissue bridges, use the manual Continuous Curvilinear Capsulorhexis technique to complete the capsulotomy.

F. POSTOPERATIVE CARE

The subject will be instructed by the operating physician on normal post-op cataract surgery instructions.

G. DATA REPORTING

A Case Report Form (CRF) binder will be used for each subject enrolled in the study. The appropriate CRF, provided under separate cover in a binder specific to this study, will be completed and signed by the investigator after each examination. All CRFs will be completed in a legible manner in ink. Any corrections will be made by drawing a single line through the incorrect entry, entering the correct information, and initialing and dating the change.

H. STUDY COMPLETION PROCEDURES

Subject Completion: Subjects are considered to have completed the study if they have completed all follow-up examinations through month 1.

Subject Termination: Subjects may be terminated from the study at the discretion of the Principle Investigator only for reasons related to the study regimen that would jeopardize the subjects' health and/or welfare if they were to continue in the study. However, every effort will be made to follow terminated subjects for safety reasons using the appropriate case report forms until the planned end of the study period.

Subjects Discontinuation/ Lost to Follow-up: Subjects may be discontinued from the study for non-study-related reasons only when no other option is possible. Reasons for discontinuation include, but are not necessarily limited to:

- 1) Voluntary withdrawal from the study by the subject;
- 2) Subject has moved from the area and is determined to be lost to follow-up;

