Although the following may be considered normal or expected events after cataract surgery, for purposes of this protocol, the following items must be documented as adverse events and evaluated accordingly:

- Anterior capsule tear

- Posterior capsule rupture with or without vitreous loss
- Choroidal effusion hemorrhage
- Corneal edema, corneal decompensation
- Corneal abrasion
- Post-operative uveitis
- Endophthalmitis
- Posterior capsule opacification
- Macular edema
- Retinal tear or retinal detachment
- Elevated intraocular pressure
- Decentered IOL
- Wound leak
- Posterior vitreous detachment
- Medication allergy or intolerance
- Ptosis
- Capsulotomy decentration
- Zonular instability
- Corneal burn
- Corneal endothelial tear
- Anterior capsule fibrosis/anterior capsule contraction syndrome

C. Evaluation

When evaluating adverse events, the investigator must determine if the event is serious, assess the severity of symptoms, the relationship of the event to the study device and study procedure, and whether or not the event was unanticipated using the following guidelines:

1. Severity

- Mild: Subject awareness of a sign or symptom that is easily tolerated, requires no treatment, and does not interfere with subject's daily activities
- Moderate: Subject awareness of a sign or symptom which may be a low level of concern to the subject and may interfere with daily activities, but can be relieved by simple therapeutic care
- Severe: A sign or symptom that interrupts the subject's daily activity and requires systemic therapy or other treatment.

2. Relationship to Study Device or Study Procedures (Causality)

- Probably: Any untoward medical occurrence reported in a subject, user, or other person, which might have a direct relationship to the study device/study protocol, including any malfunction, failure, deterioration in the characteristics or deployment and/or performance of the device, as well as any inadequacy in the labeling or the instructions for use, and an alternative cause is unlikely or significantly less likely compared to the potential

relationship to the study device/study protocol.

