Ongoing AEs and SAEs classified as “Not Related” to study device and study procedures will be treated and followed until resolution or as dictated by standard of care. Documentation in the CRF of this follow-up is not required although subject care should continue as appropriate.

2. Related AEs and SAEs

Ongoing AEs classified as “Related” to the study device and study procedures will be treated and followed until resolution or as dictated by standard of care. Documentation in the CRF of this follow-up is not required although subject care should continue as appropriate.

Ongoing SAEs classified as “Related” to the study device and study procedures will be followed until their medical endpoints are determined or until no further change in the conditions are expected.

XI. SAMPLE SIZE

A. Primary Effectiveness Endpoint - Complete Capsulotomy (At least 95% of cases)

The proposed sample size of 100 eyes, assuming a 95% success rate, will provide an exact 95% confidence interval of 88.72% to 98.36% around our point estimate.

B. Primary Safety Endpoint - Posterior Capsular Rupture & Vitreous Loss (4% or less)

The proposed sample size of 100 eyes, assuming a posterior capsular tear and vitreous loss rate of 4%, will provide an exact 95% Confidence Interval of 1.10% to 9.93% around our point estimate.

XII. DATA ANALYSIS

Continuous data will be summarized with descriptive statistics (N, mean, standard deviation, minimum, median, and maximum). Categorical variables will be summarized with N and percentage. Binary endpoints, including both primary safety and primary effectiveness, will be summarized with proportion success and associated exact (Clopper-Pearson) 95% confidence interval. All data summarized in tables will be presented in supportive line listings.

The diameter of all Zepto™ capsulotomies will be summarized as a continuous endpoint. The proportion of Zepto™ capsulotomies with anterior capsule tears or corneal touch will be reported along with its 95% exact confidence interval. The number and proportion of subjects experiencing specific adverse events will be tabulated by number and percentage of subjects experiencing those adverse events.

Hypothesis testing will not be performed. Point estimates and associated confidence intervals will be the basis of evaluation the effectiveness and safety of the device. All analyses will be performed using SAS software version 9.4

XIII. STUDY MONITORING

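### Is the time window for the anterior capsule tear proportion left open between Section VI.C and Appendix 3?

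*Protocol*

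**What the plan says.** - **Tear, Section VI.C, item 1:** "The occurrence of an anterior capsule tear will be recorded by the surgeon as a Yes or No after the completion of Zepto™ capsulotomy". No end of observation is stated.
- **Posterior rupture with vitreous loss, Section VI.B:** the item is "recorded by the surgeon as a Yes or No following the completion of surgery".
- **Order of steps, Section VII:** the study enrols subjects "who will have Zepto™ capsulotomy followed by conventional phacoemulsification and IOL implantation". Section IX.D adds: "Upon completion of the capsulotomy, the disposable Zepto™ Handpiece tip is removed from the eye". Section IX.E, step 3.15, provides: "In the event of an incomplete capsulotomy with remaining tissue bridges, use the manual Continuous Curvilinear Capsulorhexis technique to complete the capsulotomy".
- **Appendix 2:** the tear observation falls on Day 0, with no stage of the operation given. Adverse events are collected from Day 0 to Month 1.
- **Appendix 3.F:** the method for tear is observation by the surgeon in the course of the operation. Items 3.C (completeness), 3.D (corneal touch) and 3.E (posterior rupture) have the same wording.
- **Section X.B:** anterior capsule tear heads the list introduced by "the following items must be documented as adverse events and evaluated accordingly".
- **Section XII:** "The proportion of Zepto™ capsulotomies with anterior capsule tears or corneal touch will be reported along with its 95% exact confidence interval". Specific adverse events are tabulated by number and percentage of subjects, and no hypothesis is tested.

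**The concern.** Phacoemulsification and IOL implantation follow the Zepto capsulotomy in every eye, and manual completion follows in eyes with tissue bridges. A tear can first appear in any of these steps. A site that follows Section VI.C literally could close the item when the handpiece tip leaves the eye. A site that takes Appendix 3.F as the window would keep it open to the end of the operation. With up to 8 sites, the pooled proportion could mix the two.

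The tear proportion is one of the few outcomes with a planned interval, and Section XII makes point estimates and intervals the basis for judging the device. Section VI.B also names extension of an anterior tear as a recognised cause of the primary safety event. If the windows differed, the tear rate would have no single meaning, and it could fall below the tear count in the adverse-event table with no explanation.

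**Working it through.** **1. Does Appendix 3.F set a window?** The four items with the same method wording compare as follows.

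| Item | Method in Appendix 3 | Timing in Section VI |
|---|---|---|
| Completeness (3.C) | surgeon's observation in surgery | after each Zepto capsulotomy |
| Corneal touch (3.D) | same | contact by the tip while in use; recorded after the Zepto capsulotomy |
| Posterior rupture (3.E) | same | after the end of surgery |
| Anterior tear (3.F) | same | after the Zepto capsulotomy |

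Completeness and corneal touch plainly belong to the capsulotomy step. If the Appendix 3 phrase meant up to the end of the operation, both would conflict with Section VI, and they do not. The phrase says who assesses the item and how. It does not say when counting stops.

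**2. Which window does the rest of the protocol imply?** Section VI uses two recording times and gives the end-of-surgery one only to posterior rupture. Section XII counts Zepto capsulotomies with a tear and pairs tear with corneal touch, a device-step item. Both point to a capsulotomy-step rate.

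**3. What happens to later tears?** Section X.B makes them adverse events and sends all ocular adverse events to the case report form. Section X.C requires an assessment of relationship to device and procedure. Section XII tabulates them and supports the tables with line listings. Only one eye per subject is studied (Section IX.A), so subjects and eyes share the denominator of 100. The adverse-event count therefore holds every tear, however a site read Section VI.C.

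**4. Size.** Clopper-Pearson 95% limits for x of n = 100:
- lower = Beta quantile(0.025; x, n − x + 1), or 0 when x = 0
- upper = Beta quantile(0.975; x + 1, n − x)

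The protocol's own figures first. For x = 95, the lower limit is Beta(0.025; 95, 6) = 88.72% and the upper is Beta(0.975; 96, 5) = 98.36%. This matches Section XI.A: "assuming a 95% success rate, will provide an exact 95% confidence interval of 88.72% to 98.36" (percent). For x = 4 the limits are 1.10% and 9.93%, which match Section XI.B.

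The protocol gives no tear rate, so the counts below are assumptions.

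| Tears counted in 100 eyes | Exact 95% interval |
|---|---|
| 0 | 0% to 3.62% |
| 1 | 0.03% to 5.45% |
| 2 | 0.24% to 7.04% |
| 3 | 0.62% to 8.52% |
| 4 | 1.10% to 9.93% |

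Suppose 4 eyes have a tear by the end of surgery and 2 of these are first seen after the capsulotomy. The wide window gives 4/100 and the narrow one 2/100. If the two late tears fall at sites with different readings, the pooled figure is 3/100. With 0 to 4 of the 4 tears late, the narrow figure runs from 4/100 down to 0/100. Each late tear moves the estimate by 1 point and the upper limit by 1.41 points (9.93 − 8.52) to 1.83 points (5.45 − 3.62).

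Eyes with a manual completion step: at the assumed 95% success, 100 × (1 − 0.95) = 5. This counts eyes exposed to an extra step, not tears.

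**The case for a change.** The strongest case for a change is that this is a matter of data collection, which a later analysis plan cannot fully repair. Section VI.C, item 1 lacks the explicit limit that item 2 sets for corneal touch. Completion is also used loosely: Section IX.D links it to removal of the tip, while step 3.15 has the surgeon complete the capsulotomy by hand afterwards. The adverse-event assessment in Section X.C covers seriousness, severity, relationship and whether the event was unanticipated, but not the surgical step at which a tear was first seen. If sites diverged, the capsulotomy-step count could not be rebuilt with certainty. An eye could be recorded with a posterior rupture and no tear although a tear in phacoemulsification led to the rupture.

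Part of this stands. The item gives a recording time without saying outright that only tears present by then count. The rest is weaker. Divergence between sites is conjecture, and the case report form, supplied separately, may settle the point. The whole-operation count stays available because intraoperative tears are Day 0 adverse events, and an exact interval for it needs only that count and the denominator. An eye with a rupture and no tear on the capsulotomy item would still show the tear as an adverse event. Moving the planned interval to a whole-operation rate would bring in tears that arise in conventional phacoemulsification or lens implantation. That is a different quantity, and not clearly a better one for a capsulotomy device.

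**Conclusion.** The concern does not call for a change. Appendix 3.F does not contradict Section VI.C, because it states a method shared by four items. Read with Sections VI.B, VI.C and XII, the tear proportion is a capsulotomy-step rate, and tears first seen later belong to the adverse-event table. What remains is a missing detail that an analyst fills sensibly by labelling the proportion as tears seen by completion of the Zepto capsulotomy and reading it beside the adverse-event count.

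The possible shift is 1 percentage point per late tear in 100 eyes. It is zero if no tear is first seen after the capsulotomy. The protocol has no figure that would narrow this. The tear item has no target and no test, and the primary endpoints, their intervals and the sample size are unaffected. The conclusion assumes that sites record tear when Section VI.C says and document every tear as an adverse event as Section X.B requires.
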